7.4 Reporting Procedures

7.4.1 Adverse Event Reporting

The Investigator must record all observed AEs and all reported AEs. At each visit, the Investigator should ask the subject a nonspecific question (e.g., "Have you noticed anything different since your last visit?") to assess whether any AEs have been experienced since the last report or visit.

Note that any use of medication (and specifically any newly prescribed medication) during the course of a study may indicate the occurrence of an AE that may need to be recorded on both the AE and the concomitant medication page.

All AEs, serious and not serious, will be recorded on the AE eCRF page using appropriate medical terminology. Severity and relationship to study drug will be assessed by the Investigator.

When possible, clinical AEs should be described by diagnosis and not by symptoms (e.g., "cold" or "seasonal allergies" instead of "runny nose").

All AEs, whether or not related to the study drug, must be fully and completely documented on the AE eCRF and in the subject's notes.

7.4.2 Serious Adverse Event Reporting

The reporting of SAEs by the Sponsor or designee to the regulatory authorities is a regulatory requirement. Each regulatory authority has established a timetable for reporting SAEs based upon established criteria.

Serious AEs must be reported within 24 hours of discovery to the Sponsor or its designee; both using the appropriate form for initial and/or follow-up reporting and entering in the electronic data capture (EDC) system.

At a minimum, events identified by the Sponsor to require expedited reporting as serious, unexpected, and related to study drug must be brought to the attention of the responsible IRB/EC, as per applicable regulations. These will be provided by the Sponsor after their assessment. For European Union member states, the Sponsor or its designee will provide reports of suspected unexpected serious adverse reactions (SUSARs) directly to the ECs, as required by local legislation. In all other countries, it is the Investigator's responsibility to provide these expedited reports to the responsible IRB/EC. It is also the Investigator's responsibility to notify the responsible IRB/EC regarding any new and significant safety information.

When an SAE occurs, Investigators will review all documentation related to the event and will complete the paper SAE form, as well as enter the SAE into the EDC system, with all required information (for initial and/or follow-up information) and fax or email (within 24 hours of discovery) to the contact information provided on the SAE form.

Subjects will be followed through the safety follow-up period (i.e., 30[+3] days after last dose of study drug) for any SAEs and/or other reportable information until such events have resolved or the Investigator deems them to be chronic or stable.

In the event of any SAE (other than death), the study subject will be instructed to contact the Investigator (or designee) using the telephone number provided in the ICF. All subjects experiencing an SAE will be seen by the Investigator or designee as soon as is feasible following the report of the SAE.

Serious AEs occurring after the safety follow-up period (i.e., 30[+3] days after last dose of study drug) should be reported if in the judgment of the Investigator there is "a reasonable possibility" that the event may have been caused by the product.

SAEs should also be reported to the IRB/EC according to local regulations.

7.4.3 Reporting of Pregnancy

Any female subject who becomes pregnant during the study (with or without AEs) must be discontinued from the study and the pregnancy must be reported on the Pregnancy form within 24 hours of discovery to the Sponsor or its designee. Any female subject who becomes pregnant during the study will be followed through the pregnancy outcome.

If pregnancy occurs during the study, the pregnant subject should be unblinded so that counseling may be offered based on whether the fetus was exposed to the active drug or placebo.

Any AEs that are the consequence of pregnancy and which meet the criteria for serious should also be reported via the SAE form.

7.4.3.1 Reporting Paternal Drug Exposure

Paternal drug exposure is defined as a father's exposure to a medicinal product before or during his partner's pregnancy. Any paternal drug exposure cases must be reported to the Sponsor within 24 hours of discovery via the Pregnancy form. Any AEs that are the consequence of paternal drug exposure and which meet the criteria for serious must also be reported to the Sponsor within 24 hours of discovery via the SAE form.

Final Version: 1.0

7.4.4 Reporting of Overdose

An overdose is a deliberate or inadvertent administration of a treatment at a dose higher than the maximum recommended dose per protocol. It must be reported to the Sponsor or designee on the Sponsor Overdose Reporting form within 24 hours of discovery. In addition, all events of overdose are to be captured as protocol deviations (see Section 5.1.7).

8 MONITORING

Routine monitoring of study sites is described in Section 11.

Clinical site monitoring is conducted to ensure that the rights and well-being of human subjects are protected, that the reported study data are accurate, complete, and verifiable, and that the conduct of the study is in compliance with the currently approved protocol and amendment(s) as applicable, with GCP, and with applicable regulatory requirements. Details of the study site monitoring process are described in a separate clinical monitoring plan document.

9 STATISTICAL METHODS AND DATA ANALYSIS

9.1 Statistical and Analytical Plans

Statistical methods will be documented in detail in a statistical analysis plan (SAP) to be approved by the Sponsor prior to database lock. Deviations from the approved SAP, if any, will be described and justified in the final clinical study report.

9.2 Statistical Hypotheses

The primary endpoint is the Change from Baseline at Week 6 in the caregiver-rated ABC-I subscale score. The primary analysis will be based on the Full Analysis Set.

Let Δ be the difference in the mean Change from Baseline at Week 6 in the ABC-I subscale score between either pimavanserin dose group and the placebo group:

The null hypothesis for the primary efficacy endpoint is: $\Delta=0$

The alternative hypothesis for the primary efficacy endpoint is: $\Delta \neq 0$

The hypothesis testing for pimavanserin high dose versus placebo and pimavanserin low dose versus placebo will be tested in a sequential order. That is, if there is no evidence to show the superiority of the pimavanserin high-dose treatment to the placebo with respect to the primary efficacy endpoint at the significance level of 0.05, no further testing will be performed for pimavanserin low-dose treatment versus placebo.

Clinical Study Protocol Amendment 4

9.3 Sample Size Determination

The planned sample size is a total of 228 subjects for both age groups combined (76 subjects randomized to each of the three treatment groups of equal sample sizes: pimavanserin high dose group, pimavanserin low dose group, and the placebo group). The total study sample size will be comprised of at least 35% (80) subjects in the younger age group (5 through 12 years old).

Assuming the true difference in the mean change in the ABC-I subscale score from Baseline to Week 6 is 5 points between each pimavanserin dose group and the placebo group, and assuming the common standard deviation is 10 points, 64 evaluable subjects per treatment group will provide 80% power to detect the difference between either pimavanserin dose group and the placebo group at a significance level of 0.05, using a 2-sided t-test. Adjusting for a potential discontinuation rate of up to 15%, approximately 76 subjects per treatment group or 228 total subjects will be randomized.

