9.5.1.2 Primary Estimator

The primary efficacy endpoint, Change from Baseline at Week 6 in the ABC-I score, will be analyzed using MMRM model. The model will include effects for the age group (5 through 12 years old or 13 through 17 years old; categories based on age at screening), region (US or rest of world), treatment group (pimavanserin high dose, pimavanserin low dose, or placebo), visit (Week 1, Week 2, Week 3, Week 4, Week 5, or Week 6), the treatment-by-visit interaction, and the Baseline ABC-I score. An unstructured covariance matrix and Kenward-Roger approximation for the denominator degrees of freedom will be used. The primary treatment comparisons will be based on the difference in least squares means at Week 6 between each pimavanserin dose group and the placebo group using the Full Analysis Set.

A hierarchical testing procedure will be used to control the Type 1 error rate across the two treatment comparisons (pimavanserin high dose vs. placebo and pimavanserin low dose vs. placebo) for the primary endpoint. The hypotheses testing will be conducted in sequential order: 1. pimavanserin high dose versus placebo, 2. pimavanserin low dose versus placebo. If the first comparison fails to reach statistical significance at the 2-sided 0.05 level, the subsequent comparison will be declared as not statistically significant regardless of the associated nominal p-value. The study-wise Type 1 error rate will be maintained at the significance level of 0.05.

In addition to the primary treatment comparisons for the Week 6 timepoint, the treatment groups will also be compared at each of the other timepoints (Weeks 1, 2, 3, 4, and 5) using the same MMRM model described above. These other comparisons will be considered exploratory.

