10.7 Protocol Amendments

Changes to the protocol may be made only by the Sponsor (with or without consultation with the Investigator). All protocol modifications must be submitted to the site IRB/EC in accordance with local requirements and, if required, to regulatory authorities, as either an amendment or a notification. Approval for amendments must be awaited before any changes can be implemented, except for changes necessary to eliminate an immediate hazard to trial subjects, or when the changes involve only logistical or administrative aspects of the trial. No approval is required for notifications.

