2 EFFICACY ANALYSES

Section 12.4 Multiple Comparisons / Multiplicity (Page 27):

In response to the FDA's comments, the hierarchical testing procedure has been reverted to the testing procedures outlined in the previous version of the SAP, dated December 22, 2022, which is consistent with the protocol.

A hierarchical testing procedure will be used to control the Type I error rate across the two treatment comparisons (pimavanserin high dose vs. placebo and pimavanserin low dose vs. placebo) for the primary endpoint. The hypotheses testing will be conducted in sequential order: 1. pimavanserin high dose versus placebo, 2. pimavanserin low dose versus placebo. If the first comparison fails to reach statistical significance at the 2-sided 0.05 level, the subsequent comparison will be declared as not statistically significant regardless of the associated nominal p-value. The study-wise Type I error rate will be maintained at the significance level of 0.05.

Section 13.1.2.2 Tipping Point Analyses (Page 32):

In response to the FDA's comments, the tipping point analyses have been updated to remove the limitation on the delta value, allowing it to exceed 100% until the conclusion of the primary analysis is overturned.

This sensitivity analysis of the tipping point analysis will be implemented for Full Analysis Set using delta adjustment imputation. This MNAR (missing not at random) sensitivity analysis is to departure from MAR (missing at random) assumption by progressively increasing the delta until conclusion from the primary analysis is overturned. The delta value is 0% to 100%, 200%,.... in 5% increments of the observed treatment difference between a pimavanserin high dose and placebo, pimavanserin low dose and placebo, from the primary analysis of MMRM (mixed model for repeated measures) model until conclusion of the primary analysis is overturned.

Signature Page for ACP-103-069 Statistical Analysis Plan Addendum

Approval w eSig Task	PPDPPDPPD
	14-Oct-2024 17:46:04 GMT+0000
Approval w eSig Task	PPD 1cs 14-Oct-2024 17:46:43 GMT+0000
Approval w eSig Task	PPD s 14-Oct-2024 18:47:45 GMT+0000

Signature Page for ACP-103-069 Statistical Analysis Plan Addendum

STATISTICAL ANALYSIS PLAN

Protocol No.:	ACP-103-069
Protocol Title:	A Phase 2, Randomized, Double-blind, Placebo-controlled Study to Evaluate the Efficacy and Safety of Pimavanserin for the Treatment of Irritability Associated With Autism Spectrum Disorder
Drug:	Pimavanserin

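### The stated 80% power for either dose versus placebo is delivered for the high dose only; under the fixed-sequence test the low dose has about 69% on the same assumptions

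*Protocol*

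**What the plan says.** Protocol 9.3 assumes that the true Week 6 difference in ABC-I change "is 5 points between each pimavanserin dose group and the placebo group". It takes the SD to be 10 in every group. From this it concludes that "64 evaluable subjects per treatment group will provide 80% power to detect the difference between either pimavanserin dose group and the placebo group". The calculation behind that figure is a two-sided t-test at the 0.05 level. An allowance of up to 15% discontinuation brings the randomized number to 76 per group and 228 in total. The protocol synopsis and SAP 3.5 repeat the statement.

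The decision rule is given elsewhere. Under Protocol 9.2, if the high dose does not show superiority, "no further testing will be performed for pimavanserin low-dose treatment versus placebo". Protocol 9.5.1.2 fixes the order as high dose and then low dose, and says that if the first comparison fails "the subsequent comparison will be declared as not statistically significant regardless of the associated nominal p-value". The SAP Addendum, Section 2, restores this two-step procedure as the current one: "If the first comparison fails to reach statistical significance at the 2-sided 0.05 level, the subsequent comparison will be declared as not statistically significant". SAP version 3.0, Section 12.4, had the same two comparisons as its first two steps, so the point is the same under either version.

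**The concern.** The power statement covers both dose comparisons with a single figure, but the testing procedure treats them differently. The high dose is tested unconditionally at 0.05, so its stand-alone power is its actual power. The low dose must pass two tests, its own and the high dose's, so its power is the probability that both succeed. That probability is necessarily no larger than the stand-alone figure. Neither document gives it, and neither says that 80% is the power of each pairwise test before the sequence is applied.

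Low dose versus placebo is one of the two primary comparisons. If it ends as not significant, how much a reader makes of that depends on the chance the design had of showing a real effect. A reader who relies on the sample-size section would put the risk of missing a true 5-point low-dose effect at 20%. On the same inputs it is about 31%.

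**Working it through.** **Inputs.** Difference 5 for each dose, SD 10, 64 evaluable per arm, two-sided 0.05 t-test, 15% loss (all Protocol 9.3); 1:1:1 allocation with one placebo arm (Protocol 5.1.4); high dose tested before low dose (Protocol 9.5.1.2 and SAP Addendum, Section 2).

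**1. Reproduce the plan's figure.**
- Noncentrality = 5 / (10 × √(2/64)) = 2.828, with 2 × 64 − 2 = 126 degrees of freedom and critical value 1.979.
- Power from the noncentral t = 80.1%, for each dose tested alone.
- Inflation: 64 / 0.85 = 75.3, rounded up to 76; 76 × 3 = 228.

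All the stated figures reproduce.

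**2. Correlation between the two tests.** Both contrasts use the same placebo mean. With n per arm, each contrast has variance 2σ²/n and their covariance is σ²/n, so the correlation is (σ²/n) / (2σ²/n) = 0.5. This follows from the design and needs no outside assumption.

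**3. Low-dose power under the sequence.** The quantity needed is P(high dose significant and low dose significant).
- Simulating the pairwise t-tests with a shared placebo arm (runs of 1 to 4 million trials): 68.9% to 69.0%.
- Bivariate normal approximation: each margin is Φ(2.828 − 1.960) = Φ(0.868) = 80.7%, and the joint probability at correlation 0.5 is 69.7%. The normal approximation runs slightly high in both places.
- Ignoring the shared placebo arm would give 0.801² = 64.2%, which is too low.

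**4. Where the difference goes.** Low-dose p ≤ 0.05 occurs in 80.1% of trials. In 68.9% the high dose also succeeds. In the remaining 11% or so the high dose fails and the low dose must be declared not significant. Given high-dose success, low-dose power is 0.689 / 0.801 = 86%.

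**5. Sensitivity (t-test basis).**

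| Evaluable per arm | SD | True difference, high / low | Low dose alone | Low dose under sequence |
|---|---|---|---|---|
| 64 | 10 | 5 / 5 | 80.1% | 68.9% |
| 76 (no loss) | 10 | 5 / 5 | 86.5% | 78.0% |
| 64 | 9 (assumed) | 5 / 5 | 87.6% | 79.7% |
| 64 | 10 | 5 / 4 (assumed) | 61% | 55% |
| 64 | 10 | 5 / 3 (assumed) | 39% | 36% |

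In the last two rows most of the fall comes from the smaller effect, not from the sequence. For scale only, 80% low-dose power under the sequence with both differences at 5 and SD 10 would need about 79 to 80 evaluable per arm (79.9% and 80.5% by simulation).

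**The case against.** The strongest reply is that the sentence is true as a pairwise statement. It names a two-sided t-test at 0.05, Protocol 9.2 uses similar wording to define each pairwise difference, and 80.1% is right for each dose taken alone. The dependence of the low dose on the high dose is set out in the section immediately before the power statement, so nothing is hidden. Losing power on the second comparison is the ordinary price of fixed-sequence testing. Putting the high dose first is a defensible choice, because Protocol 1.4.2 selects it to reach the target exposure and presents the low dose as a chance to explore lower exposures.

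Much of this stands. The calculation contains no computing error and the design is sound. But the text never says that 80% is power before the sequence is applied, and Protocol 9.5.1.2 names both comparisons as primary. Giving one figure for two comparisons that the decision rule treats differently leaves the low-dose figure wrong in use.

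A second reply is that the planned MMRM adjusts for baseline and uses partial data from subjects who drop out, and that 15% is an upper limit on loss, so real power may exceed the t-test figure. That is fair: with an assumed SD of 9.5, low-dose power under the sequence is about 74% at 64 per arm and about 83% at 76. The same gain would raise the stated 80%, however, so the gap between the two doses remains. The 69% should be quoted on the same t-test basis as the 80%.

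**Conclusion.** The concern holds. On the plan's own assumptions (5 points for both doses, SD 10, 64 evaluable per arm, t-test), power is 80.1% for the high dose and about 69% for the low dose under the fixed sequence, a shortfall of about 11 percentage points. With no loss at all, the low dose reaches about 78%, still below 80%.

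The 69% depends on the high dose truly having a 5-point effect; a smaller high-dose effect lowers low-dose power further, whatever the low dose does. The MMRM may give higher power for both doses. Type I error control and the planned numbers of subjects are not in question. This is an error in what the plan reports about its own power, and it should be corrected.

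**What to change.** Replace the single power statement in SAP 3.5, and in Protocol 9.3 and the synopsis, with text to this effect:

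> With 64 evaluable subjects per group, power is 80% for high dose versus placebo. Under the fixed-sequence procedure, the power to declare low dose versus placebo significant is about 69% if both true differences are 5 points (t-test basis), and lower if the low-dose effect is smaller.

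Any figures added for smaller low-dose effects should be labelled as illustrative assumptions, because the documents give no such effects.

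The cost is wording and a less favourable stated figure. Sample size, test order, significance level and analysis do not change. Protocol 10.7 requires that "All protocol modifications must be submitted to the site IRB/EC in accordance with local requirements", so the SAP sentence can be corrected first and the protocol text carried with the next amendment. Until then SAP 3.5 would differ from the protocol, and a short note in SAP 19, which lists changes from the protocol, would explain why.

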9.4 Population Analysis Sets

The **Safety Analysis Set** will include all randomized subjects who received at least one dose of study drug (pimavanserin or placebo). Subjects will be analyzed based on the treatment that they actually received. The Safety Analysis Set will be used for all safety analyses.

The **Full Analysis Set** will include all randomized subjects who received at least one dose of study drug and who have both a baseline value and at least one post-Baseline value for the ABC-I subscale score. Subjects will be analyzed based on their randomized treatment. The Full Analysis Set will be used for the analysis of all efficacy endpoints.

The **Pharmacokinetics Analysis Set** will include subjects in the Safety Analysis Set with at least one measurable plasma concentration. The Pharmacokinetics Analysis Set will be used for pimavanserin and AC-279 plasma concentration summaries.

Any other analysis sets, if necessary, will be defined in the SAP.

9.5 Statistical Analyses

Continuous measurement results will be reported using the number of subjects with data values, mean, standard error of the mean, standard deviation, minimum, maximum, and median. For each categorical outcome, the number and percentage of subjects in each category will be reported.

Handling of missing values will be described in detail in the SAP.

Final Version: 1.0

9.5.1 Primary Endpoint Analysis

9.5.1.1 Estimand

The primary clinical question of interest for the primary objective is: what is the difference in the mean changes from Baseline to Week 6 in the ABC-I score comparing pimavanserin high dose versus placebo, and pimavanserin low dose versus placebo, in subjects with ASD with irritability, agitation, or self-injurious behaviors, assuming all subjects complete 6 weeks of treatment without extended use of rescue medications or use of prohibited medications?

The estimand is described by the following attributes:

Population: subjects diagnosed of ASD with irritability, agitation, or self-injurious behaviors as defined by the inclusion/exclusion criteria of the study.

Variable (primary endpoint): Change from Baseline at Week 6 in the ABC-I score.

Treatment condition: pimavanserin high dose, pimavanserin low dose, and placebo without extended use of rescue medications or use of prohibited medications.

Intercurrent events and strategies:

- The two intercurrent events (ICEs) "treatment discontinuation due to COVID-19", "treatment discontinuation not due to COVID-19" will be addressed by the hypothetical strategy (i.e., assuming that subjects with these ICEs evolve in the same way after ICE occurrence as the subjects in the same treatment group who complete the treatment).
- The intercurrent events "use of rescue medications beyond maximum allowed period" and "use of prohibited medications" (as listed in the Appendices A and B) will be addressed by the treatment condition attribute following the hypothetical strategy (i.e., considering measurements of the primary efficacy endpoint, if collected, as missing from the point of these ICE occurrence onward and assuming that subjects with this ICE evolve in the same way after ICE occurrence as the subjects in the same treatment group without these ICEs).
- The intercurrent event "remote assessments" will be addressed by the treatment policy strategy, i.e., utilizing measurements of the primary efficacy endpoint regardless of the occurrence of this ICE.
- Alternative approaches to handling intercurrent events will be addressed in the sensitivity analyses. Details on the sensitivity analyses will be provided in the SAP.

Population-level summary: difference (pimavanserin high dose vs. placebo, pimavanserin low dose vs. placebo) in the mean changes from Baseline to Week 6 in the ABC-I score.

